## ROKHYT TRIAL PROTOCOL

**The specific aims of this protocol** are to:

1. Develop and pre-test the intervention text messages.
2. Pilot the enrollment, consent, randomization, and data collection procedures at baseline and 3, 6, and 12 months and document participation and completion rates in a randomized pilot study of N=70 per group.
3. Obtain demographic data on potentially eligible participants using an on-line questionnaire.
4. Pilot test the text messaging intervention and document blood pressure control rate in response to the intervention.
5. Pilot test secure data transfer and other data coordinating center (DCC) functions.

The following metrics will be used to decide whether to proceed with a larger trial: **Aim 1**. Successful piloting of text messages including tailored features, based on positive feedback from pilot subjects. **Aim 2**. Successful enrollment, consent, and randomization of N=70/group. **Aim 3**. Completion of >80% of all data fields. **Aim 4**. Completion of 12-month follow-up by >80% of those randomized; positive signal of intervention effect. **Aim 5**. Successful and secure transfer of all pilot data from higi to the DCC.

The overall goal is to provide pilot data to support an application to conduct a fully powered randomized controlled trial.

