- \$100 at 12-month blood pressure check and final survey. All higi communications are available in English or Spanish as selected by the individual. **Eligibility** criteria are shown in table 3. **Consent** will be obtained electronically, also in English or Spanish. **Randomization** will be stratified by sex, age (18-55, 56-85 years), and region of the country (northeast, southeast, north central/west, south central/west), assigned 1:1, and performed by the DCC using the web-based trial management system. Participants will receive email informing them that they have been enrolled and which group has been assigned. **Data collection** for Aim 3 will be accomplished using an electronic form with multiple-choice or numeric response sets on the secure web portal, to be completed as part of the consent process. We will obtain BP measurements at the kiosk at time of enrollment and at 3, 6, and 12 months post randomization. For follow-up measurements, subjects will receive email messages prompting them that it is time to obtain a study BP measurement at a kiosk along with instructions about how to take the BP, specifically to take all of their usual medications the day they take the BP, to log in at the kiosk using their account identifier (email address) when they take the BP, and to take the BP three times at intervals of about one minute. Subjects will receive up to \$200 in Bank of America pay card by mail when completing each blood pressure check points. **Participation rate** will be calculated as the proportion of those invited to participate and eligible who consent and complete the baseline questionnaire and BP measurement. **Completion rate** will be calculated as the proportion of those randomized who complete the 12-month follow-up BP measurement. We do not propose to replace randomized individuals who die, drop out, or are lost to follow-up in either the pilot or the full scale study.

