**Aim 4. Pilot test the text messaging intervention and document BP control rate in response to the intervention in a pilot study of N=70 per group.** Once the intervention messages have been developed, pre-tested, and approved by our IRB, we will conduct a pilot of the study procedures using 5-10 volunteers, specifically of the enrollment, intervention, and data collection procedures. Once we are satisfied that the procedures are working as expected, we will conduct a pilot study randomizing 70 individuals to each group. We chose this sample size for the pilot as 10% of the planned full scale trial and therefore sufficient to demonstrate that all study procedures including recruitment are feasible and realistic and to provide a preliminary signal of the intervention effect. The intervention group will receive text messages as described below. The comparison group will receive usual care. Blood pressure measures will be obtained in both groups at baseline and at 3, 6, and 12 months. A reduced questionnaire will be administered at 12 months to ascertain insurance and health care provider status at that time. Compensation (up to \$200 by Bank of America pay card) will be sent by mail to all individuals who complete the blood pressure checks at 3, 6 and 12 months follow up.

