Title: Retail Outlet Health Kiosk Hypertension Trial (ROKHyT)

Registration#: NCT03515681

Protocol Version Date: 15APR2019

Statistical Analysis Plan

The overall goal of the R34 pilot grant is to develop pilot data for an application for a fully powered trial. The intervention using interactive text messaging will be compared to current information provided in the context of higi installation (usual care). The primary endpoint will be hypertension control defined as < 149/90 mmHg at 12 months post randomization. Measurements will also be obtained at 3- and 6-months post randomization.

The specific aims are shown in table 1.

Table 1. Specific Aims
1. Develop and pre-test the intervention text messages
2. Pilot the enrollment, consent, randomization, and data collection procedures at baseline and 3, 6, and 12 months and document participation and completion rates in a randomized pilot study of N=70 per group.
3. Obtain demographic data on potentially eligible participants using an on-line questionnaire.
4. Pilot test the text messaging intervention and document blood pressure control rate in response to the intervention.
5. Pilot test secure data transfer and other data coordinating center (DCC) functions.

Aim 1. No statistical analysis.

Aim 2. The numbers enrolled, consented, and randomized will be tabulated.

Aim 3. Demographic characteristics will be tabulated.

Aim 4. The proportion in each group (intervention and control) achieving blood pressure control at 12 months will be tabulated and the difference between these proportions will be calculated. Control will be defined as systolic blood pressure <140 mmHg and diastolic blood pressure <90 mmHg. A Mantel-Hanzel relative risk with adjustment for stratification will be calculated comparing the two groups. In addition, the proportions achieving blood pressure control at 3-months and 6-months follow-up will also be tabulated. Formal statistical testing will not be done because the pilot study is not powered for hypothesis testing.

Aim 5. No statistical analysis.

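### The pilot's efficacy signal for proceeding rests on two point estimates of a dichotomised outcome, reported without intervals; adding 95% CIs and a supporting baseline-adjusted systolic difference would cost little

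*Protocol*

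**What the plan says.** The protocol's opening section lists metrics for deciding whether to go on to a larger trial. The entry for Aim 4 is "Completion of 12-month follow-up by >80% of those randomized; positive signal of intervention effect". Its first half has a number; its second half has none. Under Aim 4 the protocol says the pilot should be large enough "to provide a preliminary signal of the intervention effect", and the size is justified as a share of the later trial ("We chose this sample size for the pilot as 10% of the planned full scale trial"), not by precision.

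Under Aim 4 the SAP says that the proportions "achieving blood pressure control at 12 months will be tabulated and the difference between these proportions will be calculated". It adds: "A Mantel-Hanzel relative risk with adjustment for stratification will be calculated comparing the two groups". Control at 3 and 6 months is tabulated as well. It closes with "Formal statistical testing will not be done because the pilot study is not powered for hypothesis testing".

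Neither document mentions a confidence interval, an analysis set, or a rule for a missing 12-month reading. Aim 4 and the SAP together imply that the signal is 12-month control, but neither ties that endpoint to the metric. The SAP also defines control in two ways: its opening paragraph uses a limit of 149/90 mmHg, and its Aim 4 text uses 140 mmHg systolic and 90 mmHg diastolic.

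**The concern.** This is the only metric for proceeding that concerns efficacy; the others concern feasibility, data completeness and data transfer. A pilot of this size can give only an imprecise estimate of a difference in proportions. That is acceptable if the imprecision is shown. With point estimates alone, a reader sees a size and a sign but not how weakly they separate a useful intervention from a useless one.

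The choice of outcome adds to this. Reducing blood pressure to controlled or not discards information, and the baseline reading, which the trial collects in everyone, is not used in the comparison. The planned analysis therefore gives a noisier signal than the same data could provide.

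**Working it through.** **The plan's own figures.** The documents give no power, precision or operating rate to reproduce. The size is consistent: 70 + 70 = 140.

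**Inputs from the documents.** 70 per arm, 1:1. Completion above 80% means at least 113 of 140, about 57 per arm (57/70 = 81.4%). Dropouts are not replaced. Randomization is "stratified by sex, age (18-55, 56-85 years), and region of the country", with four regions, so 2 × 2 × 4 = 16 strata.

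**Assumptions, not in the documents.** Control rate p of 30-50% (20% also checked for the sign); systolic SD 14-20 mmHg; baseline to 12-month correlation ρ of 0.3-0.6; a 3 mmHg effect; normal readings; control judged on systolic only.

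**1. Missing precision.** The 95% half-width of the difference is 1.96·√(2p(1−p)/n). The crude 95% CI at an observed RR of 1 is exp(±1.96·√(2(1−p)/(np))).

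| n per arm | p | Half-width (points) | CI at RR = 1 |
|---|---|---|---|
| 70 | 0.3 | 15.2 | 0.60-1.66 |
| 70 | 0.5 | 16.6 | 0.72-1.39 |
| 57 | 0.3 | 16.8 | 0.57-1.75 |
| 57 | 0.5 | 18.4 | 0.69-1.44 |

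**2. Sign rule, no effect.** Exact enumeration of two binomials with the same p gives P(difference > 0).

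- Equal arms, p = 0.3-0.5: 46.3-46.6% at 70 per arm, 45.9-46.3% at 57. The shortfall from 50% is half the tie probability (7-8%).
- Unequal completers (56 v 57, 58 v 55, 60 v 53, either way round), p = 0.3-0.5: 48-52%.
- Including p = 0.2, the range over all of these is 45-53%.
- Stratified Mantel-Haenszel RR > 1, simulated over 16 strata: 46-47% with arms equal within strata, about 50% when small imbalances break ties.

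**3. Sign rule, 3 mmHg effect.** At p = 0.4 and SD 16, control rises to Φ(Φ⁻¹(0.4) + 3/16) = 0.474, a gain of 7.4 points. The SE is √((0.4·0.6 + 0.474·0.526)/70) = 0.0836, so Φ(0.0737/0.0836) = 0.81; less half the ties, about 0.79. Simulation (40,000 runs) gives 0.786. Other cases: 0.756 (SD 16, 57 per arm), 0.825 (SD 14, 70 per arm), 0.728 (SD 20, 70 per arm), 0.703 (SD 20, 57 per arm). The range is about 70-83%.

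**4. Gain from adjusted systolic pressure.** To compare the measures at a similar false-go rate, require the one-sided 70% limit to exclude no effect (z = 0.524). This level is only an illustration. For ANCOVA, SE = SD·√(1−ρ²)·√(2/n).

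- SD 16, ρ 0.5, n 70: SE = 16·0.866·0.169 = 2.34 mmHg; Φ(3/2.34 − 0.524) = 0.78.
- SD 20, ρ 0.3, n 57: SE = 20·0.954·0.187 = 3.57 mmHg; Φ(3/3.57 − 0.524) = 0.62.

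Simulated rates:

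| Setting | Measure | No effect | 3 mmHg |
|---|---|---|---|
| SD 16, ρ 0.5, n 70 | Binary control | 29% | 62% |
| | Adjusted systolic | 31% | 77% |
| SD 20, ρ 0.3, n 57 | Binary control | 32% | 57% |
| | Adjusted systolic | 30% | 62% |

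The mean 95% half-width of the adjusted difference is 4.6 mmHg in the first setting and 7.0 mmHg in the second.

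**The case against.** The best defence is that this is a pilot. Its aim is to gather data for an application, the protocol's Aim 5 text says the main approach is summarization, and testing is expressly declined. All of that stands, and nothing here asks for a test. Several further objections stand too:

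- No passage says that any positive difference counts. A rate near one half is a property of any sign rule and not specific to this trial.
- If denominators are tabulated with the proportions, a reader can work out the crude interval. Only the interval for the stratified relative risk is then lost.
- Intervals alone do not change how often a given rule is met; they show how much weight the estimate can bear.
- The case for the adjusted analysis depends on an assumed SD and correlation. Eligibility selects raised readings, which may narrow the baseline spread and lower the correlation. In the unfavourable setting the gain is only about 5 points.

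Two stronger readings are tempting and should be resisted. A reader might infer that the decision to proceed is itself a coin toss. It is not: this is one metric among several, and the rates above do not describe the joint decision. A reader might also infer, from "Participants will receive email informing them that they have been enrolled and which group has been assigned" and the weekly monitoring of follow-up readings in Aim 5, that the threshold will be set to suit the results. Participants knowing their group has no bearing on when a rule is written, and the protocol does not say that the monitoring is by group.

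**Conclusion.** The concern holds as a minor, cheaply remedied weakness. The trial says it will act on an efficacy signal, and the SAP supplies that signal as point estimates of a dichotomised outcome with no stated uncertainty. Whether 15 to 18 points of unreported half-width matters depends on the rule the sponsor will apply, which is not written down. On the assumed sign rule the metric does separate no effect (about half of pilots) from a 3 mmHg effect (about 70-83%), but weakly. At a similar false-go rate, adjusted systolic pressure does better in both settings tabulated, by about 15 points in the favourable one and 5 in the unfavourable one. Control rate, SD, correlation, effect size and the 70% limit are all assumptions. The absence of intervals, threshold and analysis set can be read directly from the documents. A lenient rule is legitimate for a pilot, provided its leniency is stated.

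**What to change.** In the SAP, Aim 4:

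1. Report the 12-month risk difference and the stratified Mantel-Haenszel relative risk with 95% CIs and no test. With 140 participants over 16 strata (140/16 = 8.75 each), use a variance suited to sparse strata, such as Greenland-Robins.
2. Add a descriptive ANCOVA of 12-month systolic pressure on group and baseline systolic pressure, with its 95% CI, labelled as supporting evidence. Keep 12-month control as the primary endpoint.
3. As a secondary matter, before results by group are seen, state the measure, time point, analysis set (including how missing 12-month readings are handled) and any threshold for the signal. The level is the sponsor's choice.
4. Reconcile the two definitions of control, since a signal cannot be fixed on the endpoint while both stand.

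The cost is a few sentences and one model on readings already planned. The downside is that part of the signal is then read from an outcome other than the primary endpoint. Any threshold stricter than the sign also stops some useful interventions. In the first setting above, the illustrative limit on adjusted systolic pressure passes 77% at 3 mmHg against 79% for the sign of the binary difference (31% v 47% with no effect). In the second it passes 62% against 70% (30% v 46%).

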### **Structure and organization of the project**

The clinical coordination function and overall project leadership is in the Division of General Medicine/Department of Medicine at Columbia ([name], principal investigator).

The data coordination function (Data Coordinating Center, DCC) is in the Department of Biostatistics in the Mailman School of Public Health ([name], principal investigator).

higi is a privately owned company that supports health kiosks with blood pressure devices in Rite Aid pharmacies throughout the United States. [REDACTED]

Mytonomy is a privately owned company that makes and hosts educational videos. [REDACTED]

### **Phases of the project**

There are three phases to the project, as follows.

- A. **Pretesting of Text Messages.** We will use formative interviews conducted by telephone to iteratively test the text messages and videos.
- B. **Vanguard.** We will run 10 vanguard or pilot subjects (randomized 7 to intervention and 3 to control) through a compressed 3-month protocol involving the invitation, consent, and baseline data collection, and follow-up data collection at 1, 2, and 3 months (blood pressure only at 1 and 2 months, blood pressure and exit questionnaire at 3 months).
- C. **Trial.** We will conduct the pilot trial (N=70 in each of the two randomized groups).

## **IRB documents**

### **Study Protocol**

#### **A. Pretesting of Text Messages and Formative interviews: N = 40**

1. Invitation (Pretesting)
2. Consent (Pretesting)
3. HIPAA release for higi to give blood pressure data and email to Columbia
4. Text messages – intervention
5. Videos

#### **B. Vanguard: N = 10**

1. Invitation (Vanguard)
2. Consent (Vanguard)
3. HIPAA release for higi to give blood pressure data and email to Columbia
4. Baseline questionnaire (27 items)
5. Text messages – intervention
6. Text messages – reminders to return for 1,2, and 3-month blood pressure measurements
7. Videos
8. Exit questionnaires (one for intervention group and one for usual care group)

#### **C. Trial: N = 140**

1. Invitation (Trial)
2. Consent (Trial)
3. HIPAA release for higi to give blood pressure data and email to Columbia
4. Baseline questionnaire (27 items)
5. Text messages – intervention
6. Text messages – reminders to return for 3, 6, and 12-month blood pressure measurements
7. Videos
9. Exit questionnaires (one for intervention group and one for usual care group)

### **Notes.**

1. Participants that completed/agreed to ROKHYT consent form but didn't complete the entire enrollment process will be contacted by phone to help them with any issues then and will be sent a text messages with a link to complete the enrollment process. In addition, we will be sending the participants with this or any other issues free text (adhoc messages) on text messages.
2. The baseline and exit questionnaires, the baseline questionnaire, and the higi HIPAA release are the same in all study phases, as are the intervention text messages and videos.
3. Higi will send the Invitation by email in all three phases. The link in the email will pass individuals to the Columbia DCC website where consent will be obtained and the baseline questionnaire will be completed. A link will pass the participant to higi's third party for the HIPAA release. On completion of the HIPAA release, a link will pass the participant back to the Columbia DCC website where participants will be randomized. The text messages will be generated by the Columbia DCC.
4. In addition to the intervention text messages (intervention group only), there will be reminder text messages for both groups to return for the follow-up blood pressure measurements (study endpoints). The email at day 45 (see diagram) will use the same text.
5. The videos will be hosted on the website of Mytonomy. Columbia has a Business Associate Agreement with Mytonomy. The license for use of the Mytonomy website by study participants was purchased through a subcontract from the trial grant.

6. The links to these videos will be embedded in intervention text messages. These links have not yet been created and are not shown in the text messages but will be inserted after they have been created.
7. Mytonomy has given us permission to provide access to the videos to the IRB members and staff.  
[REDACTED]  
[REDACTED]

[use browser other than IE to access]

### **Approach to Accomplishing the Specific Aims**

**Aim 1. Develop and pre-test the intervention text messages.** We will draft sample messages (table 2) based on the Health Belief Model in English and Spanish for each component of the messaging loop, with alternatives. Based on our previous formative work, messages will be personalized and interactive. The level of personalization may change based on the pre-testing as below but preliminarily will include first name, preferred gender and language (Spanish or English).

Additionally, messages will be different based on blood pressure elevation.

**Table 2. Focus of Intervention Text Messages**

• High BP level should be followed up

• High BP can lead to health problems unless it is treated

• A health care provider should be seen to provide treatment for high BP

• Medications lower blood pressure

• Taking blood pressure medication daily is necessary for the medication to be effective

---

Overall, there will be three types of messages. The first will be educational messages that are sent to all participants. Under the health literacy paradigm of “universal precautions” these will include key educational information that would be helpful for all participants to know. The second set of messages will be interactive and will allow participants to self-tailor messages by selecting areas about which they would like to receive more information. The third set are reminder messages which act as cues to action to come in and get a blood pressure reading taken.

**Pretesting.** Email messages will be sent to randomly selected higi users who meet eligibility criteria for the trial, inviting participation. There will be a financial incentive of \$50 in Bank of America pay card for the pre-test component. Those who participate will not be eligible for the pilot. We will obtain consent for the pretesting as for the pilot. For those who consent, we will arrange in depth interviews to be conducted by telephone to pre-test the text messages and videos and to receive feedback. We will purposefully sample to include participants from all four regions of the country. We considered focus groups rather than interviews but focus groups would limit us logistically rather than allowing random selection for this phase, and would create a time and travel barrier to participation, introducing further selection. While focus groups are helpful to explore what content areas may be helpful, the goal of this pretesting phase is to obtain specific feedback on the message structure and timing. This goal is better suited to one on one interviews.

We will pre-test the messages following the protocol [name] has previously used for field-testing messages. An important focus of pre-testing will be understandability to low literacy individuals. Under the oversight of [name], the project coordinator will text participants in real-time over the phone the proposed messages and using a semi-structured interview guide ask the individual to say back in his/her own words what the message means to him or her as well as to text back a response (if appropriate; interactive text message). The interviewer will then ask participants about any problems or suggested changes. This will include all proposed messages. Participants will also be asked their opinion on timing of reminder messages for upcoming as well as missed (separately) blood pressure checks. This process will be iterative with changes made after each set of 10 interviews until no new message changes are made. We expect to conduct 40 interviews and believe that by then we will have reached saturation. All

of the research conducted by [name] and [name] described in section C.2 was conducted in English and Spanish, as will this trial.

**Aim 2. Pilot the enrollment, consent, randomization, and data collection procedures at baseline and 3, 6, and 12 months, and document participation and completion rates.**

Enrollment, consent, randomization, and data collection will be done using a web-based trial management approach interacting with the kiosk and its associated informatics infrastructure. Kiosks are installed in all 50 states, and sampling will include all kiosk locations in the U.S.

**Enrollment** will be accomplished by randomly selecting potentially eligible individuals from the higi database to receive email messages prompting them to log into higi's HIPAA-compliant, FDA approved, secure web portal. The e-mail messages will inform these individuals that they are potentially eligible for a research study on BP and that more information is available on the

portal if they are interested in participating. Individuals will in this way be able to access a short description of the study, which is that it is a randomized trial of text messaging in patients with high blood pressure, that if they participate they will need to give consent, provide a cell phone number, and have their BP measured at time the study starts and at 3, 6, and 12 months. There will be a financial incentive of \$200 in Bank of America pay card for participation divided for 3 follow-up blood pressure checks at a higi kiosk and final survey. Compensation will be as follow at each completion:

- \$50 at 3-month blood pressure check
- \$50 at 6-month blood pressure check
- \$100 at 12-month blood pressure check and final survey. All higi communications are available in English or Spanish as selected by the individual. **Eligibility** criteria are shown in table 3. **Consent** will be obtained electronically, also in English or Spanish. **Randomization** will be stratified by sex, age (18-55, 56-85 years), and region of the country (northeast, southeast, north central/west, south central/west), assigned 1:1, and performed by the DCC using the web-based trial management system. Participants will receive email informing them that they have been enrolled and which group has been assigned. **Data collection** for Aim 3 will be accomplished using an electronic form with multiple-choice or numeric response sets on the secure web portal, to be completed as part of the consent process. We will obtain BP measurements at the kiosk at time of enrollment and at 3, 6, and 12 months post randomization. For follow-up measurements, subjects will receive email messages prompting them that it is time to obtain a study BP measurement at a kiosk along with instructions about how to take the BP, specifically to take all of their usual medications the day they take the BP, to log in at the kiosk using their account identifier (email address) when they take the BP, and to take the BP three times at intervals of about one minute. Subjects will receive up to \$200 in Bank of America pay card by mail when completing each blood pressure check points. **Participation rate** will be calculated as the proportion of those invited to participate and eligible who consent and complete the baseline questionnaire and BP measurement. **Completion rate** will be calculated as the proportion of those randomized who complete the 12-month follow-up BP measurement. We do not propose to replace randomized individuals who die, drop out, or are lost to follow-up in either the pilot or the full scale study.

